Rescue Therapy: Commercially available preservative free artificial tears (AT) provided by Sponsor are not allowed during the treatment period. Per the investigator's discretion if the patient requires rescue therapy during the 8-week treatment period then they can receive artificial tears provided by the sponsor for up to four times per day. The frequency of rescue therapy must be documented in the patient's diary.

The study will be a total of 34 weeks in duration: a screening period of 2 weeks, followed by 8 weeks of treatment and a 24-week follow-up period. At the end of the screening period (at Visit 2), patients meeting the entry criteria for this study will be assigned to treatment with OXERVATE[™] 0.002% (20

mcg/mL) cenegermin-bkbj ophthalmic solution which will be known as Study Product beginning the morning following Visit 2.

Following the completion of the treatment period, patients will be followed up for an additional 24 weeks (for patients healed and non-healed [and not meeting d/c criteria] at Week 8) and will be evaluated at the end of the follow-up period. At the investigator's discretion, the subject may be seen for an Unscheduled Visit to evaluate for safety. Patients who prematurely discontinue for whatever reason will not be followed post discontinuation and should have Visit 6 assessments completed.

At Visit 1, eligible patients will be instructed to discontinue all topical ophthalmic medications and will only be allowed to use commercially available preservative free tears provided by the sponsor to be used up to four times per day during the screening period. At the conclusion of the Baseline Visit (Visit 2) eligible patients will be dispensed a 2-week supply of Study Product from the onsite freezer in a sealed bag and will be instructed to self-administer the Study Product one drop six times a day starting on the day after Day 0/ Visit 2 through Week 8 of the controlled treatment period according to the dosing schedule shown in Table 1 (Dosing Schedule).

Table 1 Dosing Schedule

TREATMENT	TREATMENT DOSING SCHEDULE*
OXERVATE™ 0.002% (20 mcg/mL) cenegermin-bkbj ophthalmic solution	Morning (8 AM)
	Mid-morning (10 AM)
	Noon (12 PM)
	Early afternoon (2 PM)
	Mid afternoon (4 PM)
	Late afternoon (6 PM)

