^{*} The above is an example. The timing of instillation can be adjusted if a patient's awakening and/or bedtime differs throughout the 8 weeks. The patient should try and keep the daily dosing schedule as consistent as possible by trying to schedule sleep and wake times. A daily dosing diary will be maintained by the subject to track compliance for each dose of study product.

A two week supply of study product will additionally be dispensed to the patients during the treatment period at Visits 3, 4 and 5/Weeks 2, 4 and 6.

Starting from Visit 2, only the study product will be allowed. Preservative free AT provided by the sponsor *will not* be used during the study product treatment period. After the 8 weeks of Study Product treatment, and during the follow up period, AT should be used only if strictly needed. The use of AT will be tracked in the daily dosing diary.

At Visit 6 (End of Treatment), patients will be assessed for corneal healing.

Completely healed patients at week 8 are defined by SPK as Grade ≤1 in the central qualifying zone via FCS (per NEI scale) and no persistent staining in the non-qualifying zones (excluding the superior zone) defined as the absence of pathological staining via corneal photography. Patients who are completely healed at Week 8 will be followed for an additional 24 weeks during the follow-up period. During the 24-week follow-up period (Weeks 9-32) the patients will be followed without any Study Product, however, preservative-free AT (provided by the study sponsor) may be used documented on the daily diary. If warranted for patient safety, the Investigator may elect to see the subject at an Unscheduled Visit(s) to evaluate the patient.

Patients who are not completely healed at week 8 are defined by SPK as Grade 2 via FCS in the central qualifying zone AND who do not meet the criteria for premature discontinuation, will also be followed for an additional 24 weeks during the follow-up period. During the 24 week follow-up period (Weeks 9-32) the patients will be followed may be treated at the physician's discretion (retreatment with OXERVATE™ 0.002% (20 mcg/mL) cenegermin-bkbj ophthalmic solution is not permitted). Any concomitant treatment must be documented on concomitant medication log. If warranted for patient safety, the Investigator may elect to see the subject at an Unscheduled Visit(s) to evaluate the patient.

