5.2. DOSE, ROUTE AND SCHEDULE OF PRODUCT ADMINISTRATION

Both OXERVATE[™] 0.002% (20 mcg/mL) cenegermin-bkbj ophthalmic solution (study product) and SYSTANE Original[®] (to be used for the screening and follow-up periods only) are to be used in this study and are for topical ocular usage only.

The Study Product will be dosed one drop (35 μ l- .70 μ g of cenegermin-bkbj/drop) 6 times a day in the affected eye(s) for 8 weeks of treatment. The timing of instillation should be adjusted if a patient's awakening and/or bedtime differs based on the suggestion above in Table 1 Dosing Schedule. An example of Dosing Instructions is also provided in the Manual of Procedures (MOP).

Instructions for First Dose:

Patients will be instructed to self-administer the study product one drop in the affected eye(s) six times a day at 2 hour intervals starting on the day after Visit 2 (Day 0-Baseline and First Study product Pick Up) of the treatment period. On Day 1, the patient will start the first dose following Table 1 Dosing Schedule. *The patient should not start therapy on the same day as Day 0/Visit 2.*

On the day of Visit 3/Week 2 (For Study Product Pick-Up), the Study Product dosed is to be instilled in the clinic by the patient at approximately 2 hours intervals according to their established daily schedule for self-administration of the study product at home and the Study Product should be taken from the kit which is dispensed at the visit. This to ensure the patient does not miss a dose during the drop off and pick up day.

Systane Original[®] (commercially available preservative free artificial tears provided by sponsor) will be used only as strictly needed during the Screening and Follow up periods. The use of Systane Original[®] will be clearly documented in the patient's study dosing diary and in the eCRF.

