carton. Patients should be instructed to try and complete therapy before last treatment appointment, so at time of end of treatment evaluation the patient should have completed the six times a day dosing on Day 56/Week 8 for Visit 6. This will require PIs and their staff to try and schedule the last visit at the end of the day, so the patient has sufficient time to complete 6 doses on the day of Visit 6.

- 6.1.6. Visit 6 (Day 56/Week 8 4 days): END OF TREATMENT OR PREMATURE DISCONTINUATION VISIT
 - 1. IDEEL
 - 2. EQ-5D-5L
 - 3. *Pregnancy Test for women of childbearing potential: Perform a urine pregnancy test and record the results
 - 4. *Concomitant Ocular and Systemic Medications Update
 - 5. *Record AE's
 - **6. Ophthalmic Examinations:** The following examination/procedures will be performed on BOTH EYES unless otherwise specified:
 - a. BCDVA
 - b. External Ocular Examination
 - c. Slit Lamp Examination
 - d. Corneal Photo Without Fluorescein
 - e. Instill Fluorescein
 - f. TFBUT
 - g. Corneal Fluorescein Staining
 - h. Corneal Photo with Fluorescein
 - i. Wait 10 minutes before performing Schirmer Test
 - j. Corneal Sensitivity
 - k. Schirmer Test Without Anesthesia (Schirmer I)
 - l. IOP
 - m. Anterior Segment OCT (selected sites)

- n. Confocal Microscopy (selected sites)
- 7. Collect used Study Product and Subject Dosing Diary
- 8. Dispense Daily Study Dosing Diary
- 9. Dispense Systane®
- 6.1.7. Visit 7 (Day 224/Week 32 ±7 days): FOLLOW-UP/FINAL STUDY VISIT
 - 1. IDEEL
 - 2. EQ-5D-5L
 - 3. *Concomitant Ocular and Systemic Medications Update
 - 4. *Record AE's
 - **5. Ophthalmic Examinations**. The following examination/procedures will be performed on BOTH EYES unless otherwise specified:
 - a. BCDVA
 - b. External Ocular Examination
 - c. Slit Lamp Examination
 - d. Corneal Photo Without Fluorescein
 - e. Instill Fluorescein
 - f. TFBUT
 - g. Corneal Fluorescein Staining
 - h. Corneal Photo with Fluorescein
 - i. Wait 10 minutes before performing Schirmer Test
 - j. Corneal Sensitivity
 - k. Schirmer Test Without Anesthesia (Schirmer I)
 - l. IOP
 - m. Anterior Segment OCT (selected sites)
 - n. Confocal Microscopy (selected sites)

- 6. *Collect Daily Study Dosing Diary
- 7. Patient will be discharged from the study

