OXERVATE is a prescription eye drop solution used to treat a condition called neurotrophic keratitis. OXERVATE is safe and effective in children two years of age and older.

Before you use OXERVATE, tell your doctor about all of your medical conditions, including if you:

- have an infection in your eye. If you get an eye infection while using OXERVATE, talk your doctor right away.
- · are using any other eye drops.
- · wear contact lenses.
- are pregnant or plan to become pregnant. It is not known if OXERVATE will harm your unborn baby.
- are breastfeeding or plan to breastfeed. It is not known if OXERVATE passes into your breastmilk. Talk to your doctor about the best way to feed your baby if you use OXERVATE.

Tell your doctor about all the medicines you take, including prescription and over-the counter medicines, vitamins, and herbal supplements.

How should I use OXERVATE?

- See the complete Instructions for Use at the end of this Patient Information leaflet for detailed instructions about the right way to use OXERVATE.
- Use OXERVATE exactly as your doctor tells you.
- Use 1 drop of OXERVATE in the affected eye or both eyes if needed, 6 times each day, about 2 hours apart starting in the morning. Continue your treatment for 8 weeks.
- If you use any other eye drops, wait at least 15 minutes before or after using OXERVATE. This will help to avoid one eye drop diluting the other eye drop.
- If you also use an eye ointment or gel or an eye drop that is thick, use OXERVATE **first**, and then wait **at least 15 minutes before** using the other eye ointment, gel, or drops.
- If you wear contact lenses in your affected eye or both eyes remove them before using OXERVATE and wait 15 minutes after using OXERVATE before reinserting them.
- If you miss a dose of OXERVATE, take your next dose at your scheduled time. **Do not** take an extra dose to make up for a missed dose.
- **Do not** use other eye medicines without talking to your doctor.
- Talk to your doctor first before you stop using OXERVATE.
- If you have any questions about how to use OXERVATE, ask your doctor or pharmacist.

What should I avoid while using OXERVATE?

Your vision may be blurred for a short time after using OXERVATE. If this happens, wait until your vision clears before you drive or use machines.

What are the possible side effects of OXERVATE?

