The most common side effect of OXERVATE is eye pain, enlarged blood vessels in the white of the eyes (ocular hyperemia), swelling (inflammation) of the eye, and increase of tears (increased lacrimation).

Tell your doctor if you have any side effects that bother you. These are not all the possible side effects of OXERVATE. Call your doctor for medical advice about side effects. You may report side effects to FDA at [name].

General information about the safe and effective use of OXERVATE.

Medicines are sometimes prescribed for purposes other than those listed in a Patient Information leaflet. Do not use OXERVATE for a condition for which it was not prescribed. Do not give OXERVATE to other people, even if they have the same symptoms you have. It may harm them.

You can ask your pharmacist or doctor for information about OXERVATE that is written for health professional.

What are the ingredients in OXERVATE?

Active ingredient: cenegermin-bkbj

Inactive ingredients: disodium hydrogen phosphate anhydrous, hydroxypropylmethyl cellulose, L-methionine, mannitol, polyethylene glycol 6000, sodium dihydrogen phosphate dihydrate, trehalose dihydrate, Water for Injection, USP, and hydrochloric acid and/or sodium hydroxide to adjust pH.

Manufactured by: Dompé farmaceutici S.p.A. [name] U.S. License No. 2074

Manufactured for: Dompé U.S. Inc.

[name]

For more information, go to www.oxervate.com or call [name]

This Patient Information has been approved by the U.S. Food and Drug Administration Revised or Issued: October 2019

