Confidential Final Version 1.0, 2021-05-20 assessments will be carried out consistently either in the morning or the afternoon (preferred time window is ± 2 hours) throughout all study visits to minimize intra-subject diurnal variability. The detailed schedule of evaluations is included in the Appendix 1.

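### Only Visit 6 is sent to the end of the day, after the sixth dose; a patient examined in the morning at baseline cannot then meet the SAP's same-time-of-day rule

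*Protocol*

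**What the plan says.** **Visit 6.** Protocol 6.1.5, the Visit 5 instructions that prepare for Visit 6, says that by the end-of-treatment evaluation "the patient should have completed the six times a day dosing on Day 56/Week 8 for Visit 6". To allow this, sites are asked to try to "schedule the last visit at the end of the day, so the patient has sufficient time to complete 6 doses". The procedures for Visits 2, 4 and 7 (Protocol 6.1.2, 6.1.4 and 6.1.7) contain nothing comparable.

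**All visits.** SAP 1.2 says that all efficacy "assessments will be carried out consistently either in the morning or the afternoon (preferred time window is ± 2 hours) throughout all study visits". The stated reason is to limit variation within a patient over the day. SAP 9 plans no changes from the protocol.

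**Dosing.** Protocol 5.2 has patients dose "six times a day at 2 hour intervals starting on the day" after Visit 2. Table 1 in Protocol 3.3 illustrates this with doses from 8 AM to 6 PM. Its footnote calls the table an example and adds: "The timing of instillation can be adjusted if a patient's awakening and/or bedtime differs throughout the 8 weeks".

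**Drops around the exams.** Baseline precedes any study product, but sponsor-supplied artificial tears are allowed up to four times a day during washout (Protocol 3.3). The package insert in Appendix 3 warns: "Your vision may be blurred for a short time after using OXERVATE".

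**The concern.** The SAP's rule guards against diurnal variation in measurements that are compared within a patient. The protocol's Visit 6 instruction works against it at Week 8, the primary time point, and only there.

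Drop exposure also differs between visits. Baseline has no study product but may follow an artificial-tear drop. Week 4 falls at an unspecified point in the two-hourly cycle. Week 8 comes after a full day's doses, and Week 32 is off product. The visit procedures in Protocol 6.1 set no interval between the last drop and the exam, and do not ask for it to be recorded.

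Schirmer, TFBUT and BCDVA are summarised as mean change from baseline in a single arm (SAP 5.2 and 5.4). No control group shares the change in measuring conditions, so a time-of-day or drop-timing difference could be read as treatment effect. BCDVA has further uses: it determines the 15-letter responder endpoint, and a loss of more than 10 letters is a discontinuation criterion (Protocol 3.3 and 6.2).

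**Working it through.** The plan gives no figure for the size of a timing effect. The check is clock arithmetic and a comparison of the texts.

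1. **Plan's own clock time.** Inputs: six doses, 2 hours apart (Protocol 5.2); first dose 8 AM (Table 1). Sixth dose = first dose + 5 × 2 h = first dose + 10 h. 8 AM + 10 h = 6 PM, which agrees with Table 1.
2. **Can Visit 6 be a morning visit?** It would have to follow the sixth dose and start before noon. The first dose would then have to be before 12:00 − 10 h = 2 AM. The SAP's morning option is not realistic at Visit 6.
3. **Earliest time for the other visits, Table 1 clock.** Read the window as at most 2 h from Visit 6, with Visit 6 at 6 PM: 6 PM − 2 h = 4 PM. If the window is instead ±2 h around a common target time, two visits may be 4 h apart, and the limit is 6 PM − 4 h = 2 PM. Neither reading admits a morning visit.
4. **Other dosing clocks.** Assume first doses from 5 AM to 9 AM. The sixth dose then falls from 3 PM to 7 PM. On the 2-hour reading the other visits can be no earlier than 1 PM to 5 PM.
5. **Illustrative gaps.** The documents give no clock times for visits, so these baseline times are assumptions. On the Table 1 clock, a 9 AM baseline differs from Visit 6 by at least 18 − 9 = 9 h, and a 1 PM baseline by at least 18 − 13 = 5 h.
6. **When a site meets the instruction.** It stands under Visit 5 (Week 6). Baseline (Day 0) and Week 4 (Day 28) have been done by then, so a site working visit by visit learns of it too late to align them.
7. **Which endpoints depend on it.** Schirmer, TFBUT and BCDVA are change scores. The primary endpoint is Grade 0 or 1 in the central zone at Week 8 (SAP 5.1), a threshold and not a change score.
8. **Sample-size figures.** The lower limits of 40% and 54% in Protocol 9.1 are unaffected. With n = 35, two-sided 95% Clopper-Pearson limits are 40.2% at 58% and 54.3% at 72%, which reproduces them.

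**The case against.** The strongest reply is that the texts do not strictly contradict each other. The protocol only asks sites to try, the SAP's ±2 hours is a preference, and Table 1 is adjustable. A site that books every efficacy visit late in the day satisfies both. This stands: the problem is an unreconciled tension, and a reader who infers that most patients cannot comply goes beyond documents that give no visit times. It does not clear the plan. The word preferred qualifies the window and not the morning-or-afternoon rule, and shifting dose times cannot rescue a morning schedule.

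A reader might also infer that Week 8 values are taken soon after a drop and baseline values are not. No interval is stated. At Visit 6 two questionnaires, one of 57 items, come before BCDVA. Schirmer follows fluorescein, photography, a 10-minute wait and sensitivity testing. Baseline is free of study product but not of artificial tears.

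An upward bias in Schirmer and TFBUT is another tempting inference. The insert lists increased tearing as a side effect, but does not say that it is a brief effect after each drop, and nothing in the documents links the product's ingredients to TFBUT. Only transient blur is supported, and it would tend to count against the product on BCDVA.

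Nor can one say that drop timing is unrecoverable. A diary tracks each dose, and the diary form, eCRF and Manual of Procedures are not available here.

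Finally, all efficacy analyses are exploratory (SAP 2.10), and evaluating patients after dosing is complete is a deliberate aim. Both points limit the weight of the issue. Neither makes the visits comparable.

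**Conclusion.** The concern holds as a failure to reconcile Protocol 6.1.5 with SAP 1.2. Any patient examined in the morning at baseline will miss the SAP's rule at Week 8 if the Visit 6 instruction is followed. On the Table 1 clock the other efficacy visits would have to be at about 4 PM or later. For assumed first doses between 5 and 9 AM, the limit runs from 1 to 5 PM. These limits assume that the window means at most 2 hours from Visit 6 and that Visit 6 starts no earlier than the sixth dose.

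The consequence is a possible mixing of time-of-day and drop-timing differences with the Week 8 changes in Schirmer, TFBUT and BCDVA. How many patients are affected is unknown. For BCDVA a short-term drop effect is documented but not quantified. For Schirmer and TFBUT neither size nor direction can be derived.

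A reader might extend the point to the primary endpoint, since staining is read at the same visit. The documents do not support this: the endpoint is a grade threshold, and nothing in them says that a recent drop or the hour of the day alters the grade.

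**What to change.** - Reconcile Protocol 6.1.5, Table 1 and SAP 1.2 into one time-of-day rule. State it before Visit 2 and apply it at Visits 2, 4, 6 and 7. If the end-of-day Visit 6 is kept, schedule the other efficacy visits at the same time of day.
- At each of these visits, record in the eCRF the time of the exam and of the last drop, whether study product or artificial tears.
- Report Week 8 BCDVA, TFBUT and Schirmer as values taken on a dosing day.

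Any timing of exams relative to dosing is for the sponsor to decide; this point asks only that the passages agree and that the times are known.

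The cost is protocol and SAP wording, two eCRF fields, and tighter appointment scheduling, with later appointments if the end-of-day Visit 6 is kept.

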6.2. EARLY WITHDRAWAL FROM STUDY

A premature discontinuation will occur when a patient who signed the ICF ceases participation in the study, regardless of circumstances, before the completion of the study protocol procedures. Patients can be prematurely discontinued from the study for one of the following reasons:

- Progression from Stage 1 to Stage 2 or Stage 3 NK, or corneal melting/perforation
- At the PI discretion patient is considered to be a non-responder (no improvement from baseline).
- In the qualifying/Study Eye, the FCS is unchanged (Grade=3) from baseline after 8 weeks of treatment in the qualifying NEI zone or there is an increase in FCS ≥1 within a non-qualifying NEI zone in the same eye.
- Decrease in BCDVA by >10 ETDRS letters
- Onset of infection (bacterial or viral)
- Protocol violation, including lack of compliance defined as <80% of doses taken based on diary documentation between treatment clinic visits.
- Withdrawal of consent
- Lost to follow-up during the treatment period (Every effort must be made to contact the patient; a registered letter must be sent)
- Study terminated by the Sponsor
- Other reasons, such as administrative reasons or pregnancy
- Development of AE or unacceptable toxicity per the investigator's discretion, precluding further therapy with the study drug.
- Severe protocol violations, such as an incorrect treatment administration, or a concomitant use of not permitted medications. Before removal, these cases should first be discussed with Dompé.

The reasons for premature discontinuation from the study will be reflected on the Study Termination Record of the CRF. For patients who prematurely discontinue, Visit 6 procedures will be completed, and these patients will be considered off study and will no longer be followed.

For patients that discontinue prematurely, the investigator should refer patients for further treatment as appropriate.

Replacement Procedures

Patients in this study who prematurely discontinue before completion of 8 weeks of treatment with OxervateTM will be replaced. Patients prematurely discontinuing during follow up treatment will not be replaced.

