2. SCHEDULE OF EVALUATIONS

	Visit 1	Visit 2	Visit 3	Visit 4	Visit 5	Visit 6	Visit 7
	Day	Day 0	Day 14	Day 28	Day 42	Day 56	Day 224
	(-14)	(±2)	(-2)	(-2)	(-2)	(-4)	(±7)
	Week -2		Week 2	Week 4	Week 6	Week 8	Week 32
Procedures	Screening	Baseline	Product Pick-Up	Treatment Follow-Up	Product Pick-Up	End of Treatme nt	Follow-up/ End of Study
ICF/HIPAA	X						
Demographics, Systemic and Ocular Medical History	X						
Collect date of Stage 1 NK initial diagnosis	X						
Pregnancy Test	X	X				X	
Record AEs	X	X	X	X	X	X	X
Concomitant Medications	X	X	X	X	X	X	X
IDEEL		X		X		X	X
EQ-5D-5L		X		X		X	X
BCDVA	X	X		X		X	X
External Ocular Examination	X	X		X		X	X
Slit Lamp Examination	X	X		X		X	X
Corneal Photography Without Fluorescein	X	X		X		X	X
TFBUT		X		X		X	X
FCS (NEI Scale)	X	X		X		X	X
Corneal Photography with Fluorescein	X	X		X		X	X
Corneal Sensitivity Testing	X	X		X		X	X
Schirmer Test (w/o Anesthesia)		X		X		X	X
IOP	X	X				X	X
Anterior Segment OCT (selected sites)		X				X	X
Confocal microscopy (selected sites)		X				X	X
Inclusion/Exclusion Criteria	X	X					
Assigned to Treatment		X					
Product Dispensation		X	X	X	X		
Collect Used/Unused Study Product			X	X	X	X	
AT Dispensation	X	-				X	
Dispense Daily Dosing Diary	X	X	X	X	X	X	
Evaluate Daily Dosing Diary			X	X	X	X	
Evaluate AT Use- in patient daily diary		X					X

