- 6.1.3. Visit 3 (Day 14/Week 2 2 days) STUDY PRODUCT PICK-UP VISIT
 - 1. *Concomitant Ocular and Systemic Medications Update
 - 2. *Record AE's
 - 3. *Collect Used/Unused Study Product, Daily Dosing Diary, and Inventory
 - **4.** *Study Product Dispensing: Patients will be supplied with a biweekly kit of Study product sufficient for 2 weeks of treatment.
 - 5. *Dispense Daily Study Dosing Diary
- 6.1.4. Visit 4 (Day 28/Week 4 -2 days): TREATMENT VISIT
 - 1. IDEEL
 - 2. EQ-5D-5L
 - 3. *Concomitant Ocular and Systemic Medications Update
 - 4. *Record AE's
 - **5. Ophthalmic Examinations:** The following examinations/procedures will be performed on BOTH EYES unless otherwise specified:
 - a. BCDVA

- b. External Ocular Examination
- c. Slit Lamp Examination
- d. Corneal Photo Without Fluorescein
- e. Instill Fluorescein
- f. TFBUT
- g. Corneal Fluorescein Staining
- h. Corneal Photo with Fluorescein
- i. Wait 10 minutes before performing Schirmer Test
- j. Corneal Sensitivity
- k. Schirmer Test Without Anesthesia (Schirmer I)
- 6. *Collect used Study product and Daily Study Dosing Diary
- 7. *Study Product Dispensing: Patients will be supplied with a new biweekly kit of Study product sufficient for 2 weeks of treatment.
- 8. *Dispense Daily Study Dosing Diary
- **9. Instructions to Patient:** Instruct the patient to return to the clinic for Visit 5/Week 6 Study product Pick-Up visit in two weeks. Further instruct the patient to return to the clinic with the Daily Study Dosing Diary and all the empty used/unused daily kit of Study Product in original carton box.
- 6.1.5. Visit 5 (Day 42/Week 6 2 days): STUDY PRODUCT PICK-UP VISIT
 - 1. * Concomitant Ocular and Systemic Medications Update
 - 2. *Record AE's
 - 3. *Collect Used/Unused Study Product, Daily Study Dosing Diary, and Inventory
 - **4.** *Study Product Dispensing: Patients will be supplied with a biweekly kits of Study product sufficient for 2 weeks of treatment.
 - 5. *Dispense Daily Study Dosing Diary
 - **6. *Instructions to Subject:** Instruct the patient to return to the clinic for Visit 6/Week 8 End of Treatment visit in two weeks. Further instruct the patient to return to the clinic with the Daily Study Dosing Diary and all the empty used/unused daily kit of Study Product in the original

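### Protocol 6.2 allows a patient with under 80% of diary doses to be taken off study, which can remove the true Week 8 result and tilt the observed-case healing rate towards adherent patients

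*Protocol*

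**What the plan says.** Protocol 6.2 opens its list of withdrawal reasons with "Patients can be prematurely discontinued from the study for one of the following reasons", so every item is a permission and not an obligation. One item is "Protocol violation, including lack of compliance defined as <80% of doses taken based on diary documentation between treatment clinic visits". A separate item covers "Severe protocol violations, such as an incorrect treatment administration" and similar cases, and asks for discussion with the sponsor before removal. The compliance item carries no such step.

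For anyone withdrawn, the Visit 6 procedures are done, and then "these patients will be considered off study and will no longer be followed". The section adds "For patients that discontinue prematurely, the investigator should refer patients for further treatment as appropriate". On replacement it says "Patients in this study who prematurely discontinue before completion of 8 weeks of treatment with OxervateTM will be replaced".

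The interval over which 80% is judged is not defined. The Schedule of Evaluations has a row "Evaluate Daily Dosing Diary" marked at Visits 3, 4, 5 and 6, which suggests two-week intervals. But among the on-treatment visits before Visit 6, only one carries the matching title, "Visit 4 (Day 28/Week 4 -2 days): TREATMENT VISIT". Visits 3 and 5 are product pick-up visits. That suggests four-week intervals.

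In the SAP:
- Section 5.1 makes epithelial healing at Visit 6/Week 8 the primary variable. It is analysed on observed cases in both the FAS and the FTS, with last- and worst-observation-carried-forward sensitivity analyses (LOCF and WOCF).
- Section 2.6.4 limits the FTS to patients treated through Visit 6.
- Section 2.5 assigns data to the nearest scheduled visit and gives no separate rule for exit examinations.

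**The concern.** The Week 8 healing rate and its confidence interval are the main result of a single-arm study. No control arm has the same removals, so nothing offsets a selection that follows adherence. Missing doses does not make a patient's eye unexaminable. The Week 8 result is lost only because the protocol lets participation end.

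If patients who miss doses heal less often, removing some of them and recruiting replacements leaves an observed-case rate that describes patients who took their drops, not all patients who started treatment. The decision is also discretionary and open-label. At Visit 4, staining is graded and the diary collected at the same visit. Nothing in the documents suggests misuse, but the rule leaves room for sites to apply it differently.

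**Working it through.** **1. The plan's own figure.** Protocol 9.1 gives lower 95% limits of 40% and 54% for 35 patients at 58% (Week 4) and 72% (Week 8) healing. Exact Clopper-Pearson limits with x = 0.58 × 35 = 20.3 and x = 0.72 × 35 = 25.2 are 40.2% and 54.3%, so the statement reproduces. The nearest whole-number Week 8 result, 25/35 = 71.4%, has an exact interval of 53.7% to 85.4%, a half-width of about 16 points.

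**2. What happens to a removed patient's exit examination.**
- *Around Week 2 or 4:* by the closest-visit rule it is not a Week 8 result. The patient has no observed Week 8 value in the FAS and is not in the FTS.
- *Around Week 6:* ambiguous. Visit 5 has no staining examination. Among visits that have one, Day 42 is 14 days from Day 28 and 14 days from Day 56.
- *Recorded as Visit 6:* Protocol 6.1.6 names Visit 6 as the premature discontinuation visit too. On this reading the patient stays in the rate with an early grade. The plan expects healing to rise from 58% to 72% between Weeks 4 and 8, so this would tend to lower the rate.

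**3. Bounds with no healing assumption.** Take 35 observed patients with 25 healed, plus k removed and replaced patients without a Week 8 value. The all-treated rate lies between 25/(35 + k) and (25 + k)/(35 + k).
- k = 2: 25/37 to 27/37 = 67.6% to 73.0%.
- k = 9: 25/44 to 34/44 = 56.8% to 77.3%.

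**4. Illustration of size.** The documents give no non-compliance rate, so adherence is an assumption. Patient adherence is taken as beta-distributed, with doses binomial given the patient. On the two-week reading an interval has 14 × 6 = 84 doses, and a breach is 67 or fewer (79.8%). On the four-week reading it has 168 doses, and a breach is 134 or fewer (79.8%). Let d be the probability of a breach found before Week 8 (any of three two-week intervals, or one four-week interval), r the share of breachers removed, h healing in all breachers (removed or kept), and 0.72 healing in the rest.

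All-treated rate = 0.72(1 − d) + hd. Observed-case rate = [0.72(1 − d) + h·d(1 − r)] / (1 − rd). The difference is

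excess = r·d·(1 − d)·(0.72 − h) / (1 − rd).

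| Mean adherence (SD) | d, two-week | Excess, r = 0.25, h = 0.6 to 0.4 | d, four-week | Excess, r = 0.25, h = 0.6 to 0.4 |
|---|---|---|---|---|
| 95% (5) | 4.5% | 0.13 to 0.35 points | 2.1% | 0.06 to 0.17 points |
| 90% (8) | 19.6% | 0.50 to 1.33 points | 12.3% | 0.33 to 0.89 points |
| 85% (8) | 38.7% | 0.79 to 2.10 points | 25.1% | 0.60 to 1.60 points |

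Worked case, 85% and two-week, h = 0.4: 0.25 × 0.387 × 0.613 × 0.32 / (1 − 0.09675) = 0.0210. If every breacher were removed (r = 1), the excess is d(0.72 − h). On the two-week reading that is 0.5 to 1.5, 2.4 to 6.3 and 4.6 to 12.4 points. With h = 0.72 or r = 0 it is zero.

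**5. What carrying forward recovers.** Suppose 9 are removed, 30% healed at exit and 50% would be healed at the true Week 8. Observed cases give 25/35 = 71.4%. LOCF gives (25 + 2.7)/44 = 63.0%. The all-treated rate is (25 + 4.5)/44 = 67.0%. LOCF signals that removals matter but misses the target from the other side.

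**6. Week 32.** Patients without a Week 8 result are not in the subset of Week 8 healers, so the loss there is limited to breaches first found at Visit 6. On the two-week reading these are 0.62%, 2.06% and 4.81% of those still on study, or about 0.2, 0.5 and 1.2 of 25 healers if every one led to removal. On the four-week reading the counts are 0.2, 0.8 and 1.8.

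**The case against.** The strongest reply is that the missing Week 8 result is less certain than it looks. Protocol 6.1.6, the instruction to do Visit 6 procedures at withdrawal, and the SAP's reference to Visit 6/Week 8 together support recording the exit examination as Visit 6. The patient then stays in the rate. This stands as a genuine second reading. It does not clear the rule, because a grade from around Week 2 or 4 is still not a Week 8 outcome.

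Second, much is already visible: LOCF and WOCF in the FAS, reasons for discontinuation, missing data by visit, compliance categories and a deviations listing. This also stands. A reader can count removals and see sensitivity to them, but cannot see how those patients were at Week 8.

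Third, the study is exploratory with no formal test, and every adherence and healing input is assumed. That limits what may be claimed.

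A reader might infer three stronger things. One is that the rule forces non-compliant patients out. It does not; the text is permissive. Another is that the healing rate is inflated by as much as 12 points. That needs 85% mean adherence, removal of every breacher and 40% healing in them, all at once, and none of these is in the documents. The third is that Week 32 durability is badly compromised. The expected loss is at most about two healers.

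**Conclusion.** The point holds as an avoidable gap. The protocol allows ending participation for under-80% diary compliance, and the patient's true Week 8 result is then not observed. On the closest-visit reading the observed-case FAS rate and the FTS both lose the patient, and the rate can lean towards adherent patients. On the Visit 6 reading an early grade is counted in place of the Week 8 one.

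Neither direction nor size can be computed from the documents. An upward bias requires the closest-visit reading and worse healing among breachers. On those terms, with one in four removed, it is about 0.1 to 2.1 points on the two-week reading and smaller on the four-week reading. That is small next to a half-width of about 16 points. It is zero with no removals or equal healing. LOCF and WOCF are partial checks. The change is worth making because it is cheap, not because the result is shown to be wrong.

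**What to change.** In Protocol 6.2, replace the compliance bullet with a rule to this effect: diary compliance under 80% in any interval between consecutive Visits 2-3, 3-4, 4-5 or 5-6 is, by itself, recorded as a protocol deviation and is not a reason to end study participation. These patients attend Visits 6 and 7 on schedule, and their observed results are analysed in the FAS. This also settles which interval the 80% applies to.

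All other withdrawal reasons, the target of 35 completers and the FTS stay as they are. No new failure rule, extra Week 32 table or adherence subset is needed.

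The cost is a short amendment, a few visits that are already in the schedule, and possibly a slightly lower reported healing rate.
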